## **BLOOD DRAW RISKS**

Some people have discomfort or pain when blood is collected. Insertion of a needle into the arm can cause some pain, swelling, bruising, and occasionally fainting reactions. Fainting reactions

are usually harmless, of short duration, and typically produce feelings of weakness accompanied by sweating, slowing of the heart rate, and an abnormal decrease in blood pressure. Rarely, there may be a small blood clot or infection at the site of the needle puncture. Very rarely, some people have suffered nerve damage.

### **POSSIBLE REPRODUCTIVE RISKS**

The risks to an unborn human fetus or a nursing child, when a parent is taking tacrolimus, are unknown. Women who are pregnant or nursing a child will be excluded from participating in this study. Female subjects will be asked to confirm to the best of their knowledge that they are not currently pregnant and that they do not intend to become pregnant during the study. Females of non-childbearing potential are defined as women who are postmenopausal (have not had a period in the past 12 months) or surgically sterile. For women who can still have children and who are not abstinent, 2 types of birth control will be required during participation in the study and for 6 weeks after stopping the study drug. If the subject is not abstinent and unable or unwilling to use 2 types of birth control during the study, she will not be allowed to enter the study. Women who use hormonal contraceptives will be informed that the medications used in this study may reduce the levels of the hormones in the blood, which could make that form of birth control not work as well. For this study, acceptable forms of birth control are double-barrier methods (a condom plus a diaphragm or a condom plus a cervical cap, always used with a spermicide), hormonal contraceptives (injected, implanted, or birth control pill) used with another method, or an intrauterine device (Copper T, IUD) used with another method.

Male participants in this study must be willing to use the double-barrier method of birth control with their partners.

Subjects will be instructed to notify their study doctor immediately if they become pregnant or if their female partner becomes pregnant. If a subject becomes pregnant during the study, she will be immediately withdrawn and standard of care will be determined by her treating physician, based on her condition and medical need. The subject or the subject's partner will be asked to sign a new consent form so the sponsor can collect follow-up information. The pregnancy will be monitored by the study doctor until after the birth.

**1.4.2. Overall Benefits:** Subjects may or may not receive a direct health benefit from participating in this study. They may learn more about what they think and feel about their transplant and medications and be able to track how those feelings and attitudes change over time during the study. Participation in this study will help to gather information about generic tacrolimus, which may be used in the future to improve the care of transplant patients.

## **2 STUDY OBJECTIVES**

### **2.1 Primary Objectives**

Evaluation of time to a composite event, which is defined as the time to first occurrence of acute rejection, or graft failure, or death in brand versus generic arms.

### **2.2 Secondary Objectives**

Will compare in the brand versus generic arms:

- Graft rejection at 1 year after transplant
- Graft failure at 1 year after transplant
- Death at 1 year after transplant
- Loss-to-follow-up at 1 year after transplant
- Incidence of infectious episodes at 1 year after transplant
- Incidence of malignancy at 1 year after transplant
- Adherence with medication regimen

## **3 STUDY DESIGN AND EVALUATION**

### **3.1 Study Design**

A prospective, randomized, open-label, multicenter, parallel, observational study to compare the safety and efficacy of brand versus generic tacrolimus in 200 kidney transplant recipients over a one-year follow up period. All subjects will receive other immunosuppressive medications including induction therapy (thymoglobulin, basiliximab, or no induction) and maintenance, including mycophenolate mofetil and corticosteroid therapy as directed by standard-of-care at each center. Their medication information will be recorded in their study files.

The Phase 1 portion of this study consist of 2 Arms:

Arm 1: Brand Tacrolimus (Prograf) for entire study duration (12 months)

Arm 2: Generic Tacrolimus for entire study duration (12 months)

Additionally, the study consists of 2 Phases:

Phase 1: Subjects have been randomized into either Arm 1 or Arm 2 medication. Once 40 subjects have been enrolled onto Phase 1, Phase 2 will commence.

Phase 2: Subjects will no longer be randomized. All subjects will be enrolled onto generic tacrolimus because they have elected to receive generic tacrolimus (standard of care from the subject's insurance).

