## 4 STATISTICAL METHODOLOGY

### 4.1 Dataset descriptions

For all subjects enrolled in the study, data sets will be generated and updated at each study visit based on information collected during routine clinical care visits. Data to be collected from routine clinical care will include:

Donor variables: Age, sex, race, ethnicity, Human Leukocyte Antigen (HLA) data, Blood type, Cause of death (if applicable), Cold ischemic time, Donor crossmatch results, Donor serologies (CMV, EBV Hepatitis B and C), DCD and ECD donor status, Cadaveric or living (related or unrelated) donor

Recipient variables: Age, sex, race, ethnicity, HLA data, Blood type, Transplant date, Recipient serologies (CMV, EBV Hepatitis B and C), Medical history including presence of diabetes mellitus, PRA, single antigen testing, and generic drug supplier.

Medications: induction immunosuppression, maintenance immunosuppression, treatment for rejection and concomitant medications.

Post-transplant follow-up: Rejection diagnosis (grade and method of confirmation) and date, Graft status and date of failure (if applicable), Cause of graft failure (if applicable), Death and Cause of death (if applicable), Dates of hospitalizations, Biopsy results and dates, Single antigen testing results and dates, as well as Episodes of infection, including type of infection, type of organism, treatment, and response to treatment..

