#### **4.2 Statistical Analyses (Aim 1 only)**

The primary research hypothesis states that subjects receiving generic tacrolimus (Arm 2) would exhibit a 1-year survival rate non-inferior at a 26% margin to the rate among subjects receiving brand tacrolimus (Arm 1). The primary efficacy endpoint will be analyzed as time-to-event, with follow-up time measured in days, from the date of transplant to the date of composite endpoint. Statistical testing of time until composite event will be done for the intention-to-treat population. A Cox regression analysis (adjusting for transplant center via indicator variables) will be used to test the null hypothesis that  $H_0: HR \geq HR_0$  versus the alternative hypothesis  $H_1: HR < HR_0$  where  $HR_0$  is hazard ratio of the generic group over the brand group at the margin set at 3.54 (i.e., a 26% non-inferiority margin). The null hypothesis will be rejected if the upper bound of the 90% 2-sided confidence interval (corresponding to a 5% one-sided significance level) for HR is less than 3.54.

Secondary analyses are described next but all are considered exploratory since formal testing of hypotheses is considered dubious given the small sample sizes of stratified subjects. Additional Cox models that include indicator functions for the generic arm (with brand serving as baseline) and/or stratification based on age/race covariates will be used to estimate specific hazard ratios with 95% confidence intervals to evaluate differences among recipients in Arm 2 and risk groups. Also, individual analyses of single endpoint hazard ratios (graft rejection, failure, death) as well as point and interval estimates of group-specific survival rates at 1-year (via Kaplan-Meier and Greenwood methods) are planned without adjustment for multiple comparisons.

Standard descriptive summaries will also be used to report and compare adherence (as measured with daily medication diaries, and with the coefficient of variation of tacrolimus in subjects' blood) and immunologic endpoints (measured by the production of donor specific HLA antibodies).

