## 6.2 Study Therapy

**6.2.1 Clinical Sites:** Kidney recipients will be enrolled at UCLA, UCSD, UCI, UC Davis Medical Centers. Mechanistic studies will be performed utilizing specimens collected from all sites. Adherence will be measured with daily medication diaries, and with the coefficient of variation of tacrolimus in subjects' blood.

**6.2.2 References and comparator arms:** During phase 1 of study, following consent and randomization, the control group were prescribed brand tacrolimus and the comparator group was prescribed generic tacrolimus. The study drugs were prescribed upon discharge, but no later than 14 days after transplant. Subjects continued to receive study drug for up to one year post-transplant. During phase 2 of study, generic tacrolimus will only be prescribed as part of their regular care upon discharge but no later than 14 days after transplant.

**6.2.3 Provision of investigational drugs:** We anticipate that brand and generic tacrolimus will be provided for the entire study period for Phase 1 of the study. Generic tacrolimus will be obtained by the subject through their insurance for Phase 2 only. (See letters from Astellas - Appendix 5)

**6.2.4 Number of subjects and sample size justification:** We plan to enroll a total of 200 subjects between the four sites. Of the 200 kidney recipients at least 20 will be African American recipients. 40 randomized subjects will be on Brand and 160 subjects will be on generic.

**6.2.5 Eligible Subjects:** In Phase 1, eligible subjects will be initially randomized using a ratio of 2:1 (Brand:Generic) until 40 subjects have been enrolled into the brand medication arm (Arm 1) and 20 have been enrolled into the generic medication arm (Arm 2). In Phase 2, 140 additional eligible subjects will be enrolled without randomization onto generic tacrolimus only as part of their regular care. All subjects will be followed for 1-year post-transplant. (A split-phase randomization process is necessary due to a limited supply and narrow expiration-time window associated with the Brand medication product.)

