### **6.2.8 Study regimens:**

Eligible and consented subjects will be randomized into the 2 groups below:

Arm 1 (n=40) will receive brand tacrolimus for the entire study

Arm 2 (n=160) will receive generic tacrolimus for the entire study

According to their standard practice and attending physician and surgeon recommendation, subjects should also be on a maintenance regimen consisting of any of the following medications: mycophenolate mofetil, mycophenolate sodium, corticosteroids, azathioprine. Concomitant belatacept administration is not permitted. To minimize confounding factors, efforts will be made between UCSD, UCI, UC Davis, and UCLA to synchronize a similar organ specific maintenance immunosuppressive regimen across the four sites. However, each subject's maintenance regimen will ultimately be at the discretion of the treating physician. The tacrolimus level will be maintained between 4-11 ng/dL during the duration of the study.

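### The primary Cox model adjusts for centre only, so a within-centre change in induction between the randomised and non-randomised phases would bias any comparison that includes Phase 2 subjects

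*Combined protocol and SAP*

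**What the plan says.** **Background therapy.** Section 3.1 states "All subjects will receive other immunosuppressive medications including induction therapy (thymoglobulin, basiliximab, or no induction) and maintenance, including mycophenolate mofetil and corticosteroid therapy", and leaves the choice to each centre's standard of care. Section 6.2.8 adds that "each subject's maintenance regimen will ultimately be at the discretion of the treating physician". The only alignment step is an effort in section 6.2.8 to "synchronize a similar organ specific maintenance immunosuppressive regimen across the four sites"; it does not mention induction.

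**Allocation.** Section 6.2.5 randomises 2:1 "until 40 subjects have been enrolled into the brand medication arm (Arm 1) and 20 have been enrolled into the generic medication arm (Arm 2"). Phase 2 then adds 140 generic subjects without randomisation and no brand subjects. Section 6.2.7 stratifies the Phase 1 randomisation by site, ethnic group and age, not by induction.

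**Data and model.** Section 4.1 lists among the collected data "Medications: induction immunosuppression, maintenance immunosuppression, treatment for rejection and concomitant medications". The primary test in section 4.2 is "A Cox regression analysis (adjusting for transplant center via indicator variables"). The exploratory models in 4.2 add only age and race. No planned analysis uses induction, phase or calendar time.

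**Analysis set.** The Synopsis limits the intention-to-treat population to randomised patients who took at least one dose. Sections 3.4 and 6.2.8 count all 200 subjects.

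**The concern.** Arm and phase are almost the same variable: every brand subject is in Phase 1, and 140/160 = 87.5% of generic subjects are in Phase 2. Induction is given to prevent rejection, which is one of the three components of the primary endpoint. Centre indicators remove stable differences between centres, but not a change inside a centre between phases. One centre is projected to supply 130 of the 200 subjects (Table 2), so a change there would dominate.

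The bias could run either way. If induction use rose in Phase 2, the generic arm would look better for a reason unrelated to the product, and a product at the margin could pass too often. If use fell, a truly equivalent generic would be penalised.

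**Working it through.** **1. The plan's own figure.** Section 3.4 gives 25 events (6 brand, 19 generic) from 50:150, margin 3.54, true hazard ratio 1, alpha 0.05 (one-sided by section 4.2) and power above 80%. Table 1 gives 5% dropout over 12 months.
- Event hazard: -ln(0.87) = 0.139 per year. Dropout hazard: -ln(0.95) = 0.051.
- P(event in 1 year) = 0.139/0.190 × (1 - exp(-0.190)) = 0.127.
- Events: 50 × 0.127 = 6.3 and 150 × 0.127 = 19.0, total 25.4.
- Power = Φ(√(25 × 0.25 × 0.75) × ln 3.54 - 1.645) = 86%.

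The figure reproduces. With the 40:160 split of sections 6.2.4 and 6.2.8, 25 events give Φ(√(25 × 0.2 × 0.8) × ln 3.54 - 1.645) = 81%, with only about 5 brand events (40 × 0.127).

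**2. Size of the bias, closed form.** Let induction multiply the hazard by h, with use p1 in Phase 1 and p2 in Phase 2. Use in the generic arm is pg = (20 p1 + 140 p2)/160. The hazard ratio is then multiplied by about b = (1 - pg(1 - h))/(1 - p1(1 - h)).

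At a true hazard ratio of 3.54, the generic event probability is 0.493/0.544 × (1 - exp(-0.544)) = 0.380, or about 60.8 events. So SE = √(1/5.07 + 1/60.8) = 0.462, and false non-inferiority = Φ(-ln b/0.462 - 1.645). This ignores the small effect of b on the event count.

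The documents give neither shares nor effect. Assume h = 0.5 and p1 = 40%:

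| p2 | pg | b | False non-inferiority |
|---|---|---|---|
| 40% | 0.400 | 1.000 | 5.0% |
| 50% | 0.4875 | 0.945 | 6.4% |
| 60% | 0.575 | 0.891 | 8.2% |
| 70% | 0.6625 | 0.836 | 10.4% |

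**3. Cox simulation.** With so few brand events the Wald test runs slightly above nominal even without a shift, so the comparison must be with equal use, not with 5%. The 20- and 30-point rows and the power rows come from 40:160, 13% brand events, exponential times, censoring at one year, no dropout, two induction classes and 4,000 runs per scenario. The 10-point row comes from 1,200 runs with four centres and 5% dropout.

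| Assumed change in use | Hazard factor | Unstratified | Stratified by induction |
|---|---|---|---|
| *False non-inferiority, true HR 3.54* | | | |
| none | 0.5 | 6.5-6.6% | 6.0-6.1% |
| +10 points | 0.5 | 8.4% (8.2% with centre indicators) | not run |
| +10 points | 0.7 | 7.4% | not run |
| 40% to 60% | 0.5 | 10.1% | 5.2-5.6% |
| 40% to 70% | 0.5 | 11.8-14.4% | 5.8-6.7% |
| 40% to 70% | 0.7 | 8.9-9.5% | 5.5-6.3% |
| *Power, true HR 1* | | | |
| none | 0.5 | 73% | 73% |
| 70% to 40% | 0.5 | 64-65% | 72% |

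Ranges are from separate sets of runs. In the 40% to 70% row with factor 0.5, the lower unstratified figure keeps the 20 Phase 1 generic subjects at Phase 1 use. A further repeat gave 11% rather than 10.1% for the 20-point rise.

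Centre indicators do not remove the effect. With them in the model and use rising from 50% to 90% (factor 0.5; 2,000 runs), false non-inferiority was 15.4%; adding an induction term brought it to 4.6%.

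**4. Randomised subjects only.** 40:20 gives 60 × 0.127 = 7.6 events, and power Φ(√(7.6 × 2/9) × ln 3.54 - 1.645) = 50%.

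**The case against.** **The primary set may exclude Phase 2.** Read literally, the Synopsis definition leaves a randomised 40:20 comparison with no phase confounding. This stands, and it makes the point conditional on the analysis set. But that set has about 8 events and about 50% power, and sections 3.4 and 6.2.8 count all 200, so the documents do not settle the matter.

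**No shift is documented.** This also stands. A reader might infer that induction practice did change, or that the primary result is biased. The documents show neither: they give no induction mix, effect or trend, and they aim to enrol everyone within 12 months, which limits drift. Under a 10-point shift the excess over equal use is only one or two points.

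**Physician discretion.** A reader might take the discretion clause in 6.2.8 to cover induction. It concerns maintenance only; 3.1 ties induction to centre standard of care.

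**Rejection as the dominant component.** A reader might assume this, but the documents give only a composite 13%, without a split.

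**Stratification may not repair the bias.** The return to about 5-7% depends on induction being the only difference between phases and unrelated to patient risk. With an assumed unmeasured risk factor that makes induction more likely (use 40% to 70%, factor 0.5), false non-inferiority fell only from 12.9% to 9.8% when high risk doubled the hazard, and from 13.3% to 12.5% when it tripled it. With constant practice but fewer high-risk subjects in Phase 2 (50% to 30%, hazard tripled), it was 10.9% either way. Section 3.1 also says that Phase 2 subjects elected generic through their insurance, which induction strata do not address.

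**Maintenance wording.** The list in 3.1 can be read as illustrative, with 6.2.8 as the operative text. The mismatch is a wording matter and would not carry a concern alone.

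**Conclusion.** The gap is real but bounded. A recorded variable, fixed around transplant, is left out of the model although arm and phase nearly coincide and centre adjustment cannot absorb a within-centre change. If Phase 2 subjects are in the analysis and induction halves the hazard, false non-inferiority moves from 6-7% to about 8%, 10-11% or 12-14% for rises of 10, 20 or 30 points. With the hazard cut by 30%, a 10-point rise gives about 7% and a 30-point rise about 9%. A 30-point fall costs about 8 points of power. Every share and effect here is assumed.

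A reader might conclude that induction stratification makes the pooled comparison sound. The documents do not support that: Phase 2 is not randomised, and other differences between phases would remain.

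**What to change.** 1. State in section 4.2 whether the primary set is the randomised subjects or all 200, and align the Synopsis, 3.4 and 6.2.8 with it. The 50:150 and 40:160 splits need the same reconciliation.
2. For any set that includes Phase 2 subjects, stratify the Cox model by induction type as given at transplant (thymoglobulin, basiliximab, none), with a rule set in advance for merging sparse classes. Keep the centre indicators.
3. Tabulate induction and discharge maintenance for Phase 1 brand, Phase 1 generic and Phase 2 generic, beside the primary result.
4. Show the randomised-only 40:20 estimate next to the pooled one.
5. State that stratification removes bias from measured induction only, not from patient risk or the election of generic through insurance, and does not restore a randomised comparison.
6. Separately, reconcile the maintenance wording in 3.1 and 6.2.8.

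The cost is SAP wording, one table and one extra estimate, from data already collected. Sparse strata lose a little information, but simulated power did not fall materially: about 73% with and without stratification under equal use, and 72.0% against 71.5% in runs with three strata plus centre indicators.

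### Section 3.1 ends randomised enrolment at 40 subjects in total, but 6.2.5 ends it at 60 (40 brand, 20 generic); only the 6.2.5 rule fits the plan's 200 subjects and 40/160 arms

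*Combined protocol and SAP*

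**What the plan says.** Section 3.1 describes two phases. The first is randomised: "Phase 1: Subjects have been randomized into either Arm 1 or Arm 2 medication". The second assigns everyone to generic tacrolimus without randomisation. The switch is set by one sentence: "Once 40 subjects have been enrolled onto Phase 1, Phase 2 will commence".

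Section 6.2.5 gives a different switch. Subjects are randomised 2:1, brand to generic, "until 40 subjects have been enrolled into the brand medication arm (Arm 1) and 20 have been enrolled into the generic medication arm". It continues: "In Phase 2, 140 additional eligible subjects will be enrolled without randomization onto generic tacrolimus only". It explains the split by limited brand supply with a short expiry window.

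The arm sizes appear again elsewhere. Section 6.2.4 gives 200 subjects, 40 on brand and 160 on generic. Section 6.2.8 agrees: "Arm 1 (n=40) will receive brand tacrolimus for the entire study", with 160 in Arm 2. Section 3.4, the power section, uses neither split. It assumes 50 brand and 150 generic, 25 events (6 and 19), a non-inferiority hazard ratio of 3.54 and a true hazard ratio of 1.0, and claims more than 80% power.

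**The concern.** Both closing rules cannot be followed. Read literally, 3.1 stops randomisation at the 40th subject of either arm, while 6.2.5 continues to the 60th. No brand is assigned once Phase 2 opens, so a brand arm cut short in Phase 1 could not be made up later.

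The threshold controls more than allocation. Sections 3.5 and 3.6 limit the DSMB and its monthly safety review to Phase 1, and 6.2.3 provides study-supplied drug in Phase 1 and insurance-supplied generic in Phase 2. Subjects 41 to 60 would be randomised, under DSMB review and supplied by the study under one section, and none of these under the other. The brand arm is the smaller arm and limits the precision of the hazard ratio, so a shorter Phase 1 would also cost power.

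**Working it through.** **Inputs.** Cap of 40 in Phase 1 (3.1). Ratio 2:1, per-arm counts 40 and 20, and 140 in Phase 2 (6.2.5). Planned arms 40/160 (6.2.4, 6.2.8). Event proportion 13% at one year, 25 events, margin 3.54 and true hazard ratio 1.0 (3.4). Dropout 5% (Table 1). One-sided 5% test by way of the 90% confidence interval (4.2).

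**1. Reproduce the plan's own figures.** The yearly hazard is −ln(0.87) = 0.139, and 5% dropout is −ln(0.95) = 0.051. The probability of an observed event is 0.139/(0.139 + 0.051) × (1 − e^−(0.139 + 0.051)) = 0.127. Then 200 × 0.127 = 25.4 events, or 6.3 brand and 19.0 generic at 50/150, against the stated 25 (6 and 19).

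Power = Φ( ln 3.54 / √(1/E_b + 1/E_g) − 1.645 ), where E_b and E_g are the expected brand and generic events and ln 3.54 = 1.264. At 50/150 with 25 events, E_b = 6.25 and E_g = 18.75. The standard error is 0.462, and power is Φ(2.737 − 1.645) = 86.3%. This agrees with the plan's claim of more than 80%.

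**2. Add up each closing rule.**

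| Rule | Randomised | Plus 140 | Brand / generic |
|---|---|---|---|
| 6.2.5 | 40 + 20 = 60 | 200 | 40 / 160 |
| 3.1 as worded, with the 2:1 ratio of 6.2.5 | 40 (26.7 + 13.3) | 180 | about 27 / 153 |

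Only the first row gives the 200 total and the 40/160 split. Under the second, reaching 200 would need 160 subjects in Phase 2, giving about 27/173.

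**3. Power by the normal approximation, 25 events.**

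- 40/160: E_b = 5, E_g = 20, standard error 0.500, power Φ(2.528 − 1.645) = 81.1%.
- 27/173: E_b = 3.4, E_g = 21.6, standard error 0.585, power Φ(2.160 − 1.645) = 69.7%.
- If Phase 2 stays at 140 (27/153, 22.8 to 23.4 events), power is also about 70%.

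**4. Power by enumeration.** With so few brand events the approximation is optimistic. Take independent binomial events at 13% per arm. Estimate the log hazard ratio from the two one-year cumulative hazards, with variance 1/x_b + 1/x_g, where x_b and x_g are the observed event counts. Count a success when the upper 90% bound is below 3.54, and count no brand events as a failure. Dropout and centre adjustment are left out. Power is about 63% at 27/173, 73% at 40/160 and 79% at 50/150.

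**5. Other consequences.** Expected brand events at 13% are 40 × 0.13 = 5.2 against 27 × 0.13 = 3.5. The chance of no brand event is 0.87^40 = 0.4% against 0.87^27 = 2.3%. The non-randomised share of the generic arm is 140/160 = 88% against about 160/173 = 92%.

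**The case against.** The strongest reply is that the document nearly settles the matter itself. Section 6.2.5 is the only place that gives the ratio, the per-arm stopping counts, the Phase 2 size and the reason for the split, and 6.2.4 and 6.2.8 agree with it. Section 3.1 is a short overview whose 40 equals the brand count. This stands, and it makes a dropped arm label the likely explanation. But the sentence does not say so, and it sits in the section that defines the design.

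A reader might infer that the trial will end with about 27 brand subjects. The documents do not support that. Section 3.1 gives no ratio, so 27 arises only by joining its cap to the ratio in 6.2.5 while ignoring the stopping counts in that same sentence. Stratified blocks could also move the split by a few subjects.

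A reader might also infer that 40/160 is the basis of the power claim and lies safely above 80%. Neither holds. Section 3.4 uses 50/150, and 40/160 clears 80% only by the approximation.

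Finally, 3.1, 6.2.2 and 6.2.7 use the past tense in places, so Phase 1 may already be closed. Other sentences use the future tense, so closure is not established. If it has closed, the rule no longer governs allocation, but the numbers actually randomised still have to be stated.

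**Conclusion.** The threshold in 3.1 is wrong as written and should be fixed. It conflicts with 6.2.5, and only the 6.2.5 rule is consistent with the 200 subjects and the 40/160 arms. The correction is more than clerical, because the sentence decides when randomisation and DSMB cover end.

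The size is conditional. If the 3.1 cap were applied with 2:1 allocation, randomised subjects and brand subjects would each fall by a third (60 to 40, and 40 to about 27), and power would fall by roughly 10 points relative to 40/160. That difference appears under both methods; the absolute power levels depend on the method. The shift towards non-randomised generic subjects is small, since most of that arm is non-randomised under either rule. All power figures pool randomised and non-randomised generic subjects, as the plan does, and assume 13% events and a true hazard ratio of 1.0.

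**What to change.** In 3.1, replace the switching sentence with one saying that Phase 2 opens when Arm 1 has 40 subjects and Arm 2 has 20 (60 randomised), and that 140 more then enter on generic tacrolimus.

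If Phase 1 has closed, state instead the number actually randomised to each arm in 3.1, 6.2.4, 6.2.5 and 6.2.8, and set the Phase 2 target at 200 minus the total randomised.

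In either case, restate the events and power in 3.4 for the arm sizes actually used. At 40/160, 25 events divide as 5 and 20 instead of 6 and 19. The claim of more than 80% should be rechecked by a method suited to so few events.

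The cost is a protocol amendment: one sentence in 3.1 and a recalculated paragraph and table in 3.4, or edits to four sections plus 3.4 if Phase 1 has closed. Neither route adds subjects beyond the planned 200, and neither adds procedures.
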